## List of Abbreviations

Abbreviations	Definitions
Ab	Antibody
Abcam	monoclonal anti-Brachyury antibody
ADR	adverse drug reaction
AE	adverse event
AESI	adverse event of special interest
ALT	Alanine Aminotransferase
AST	Aspartate Aminotransferase
BPI-SF	Brief Pain Inventory (Short Form)
BUN	Blood Urea Nitrogen
CBC	Complete Blood Count
CR	Complete Response
CT	Computed Tomography
CTCAE	Common Terminology Criteria for Adverse Events
CTV	Clinical Target Volume
DC	Dendritic Cells
DL	Dose Level
DSMB	Data and Safety Monitoring Board
DVH	Dose Volume Histograms
ECG	Electrocardiogram
ECOG	Eastern Cooperative Oncology Group
eCRF	electronic Case Report Form
EDC	electronic data capture
ELISA	Enzyme-linked Immunosorbent Assay
FAS	Full analysis set
FOCBP	Females of child-bearing potential
FPV	Fowlpox virus
GCP	Good Clinical Practice
GyRBE	Gray relative biological effectiveness
GM-CSF	Granulocyte Macrophage Colony-Stimulating Factor
GTV	Gross Target Volume
HIPAA	Health Insurance Portability and Accountability Act of 1996
HIV	human immunodeficiency virus
HCG	Human Chorionic Gonadotropin
HSA	Human Serum Albumin
ICF	Informed Consent Form
ICH	International Conference on Harmonization
IEC	Independent Ethics Committee
IFN	type I interferon
IHC	Immunohistochemistry
IMP	investigational medicinal product
IRB	Institutional Review Board
IV	Intravenous
LTIB	Laboratory of Tumor Immunology and Biology
MOI	Multiplicity of Infection
MRI	Magnetic resonance imaging
MVA-WT	wild-type MVA
NCI	National Cancer Institute

Abbreviations	Definitions
NK	Natural Killer
ORR	Objective Radiographic Response Rate
PBMC	Peripheral Blood Mononuclear Cells
PD	progressive disease
PFS	Progression Free Survival
PHI	Protected Health Information
PI	Principal Investigator
PR	Partial Response
PRNT	Plaque Reduction Neutralization Test
PTV	Planning Target Volume
RECIST 1.1	Response Evaluation Criteria in Solid Tumors 1.1
RT-PCR	Reverse-Transcription Polymerase Chain Reaction
SAE	Serious Adverse Event
SBRT	Stereotactic Body Radiotherapy
SC	subcutaneously
TAA	Tumor Associated Antigen
TBNK	T-cell, B-cell, and Natural Killer Cell Quantitation by Flow Cytometry/Lymphocyte surface marker analysis
TEAE	Treatment-Emergent Adverse Events
TRICOM	TRIad of COstimulatory Molecules
TSH	Thyroid stimulating hormone

## 1.4 Protocol Synopsis

Title	A Phase 2 Trial of BN-Brachyury and Radiation Therapy in Patients with Advanced Chordoma
Clinical phase	Phase 2
Sponsor	Bavarian Nordic A/S [REDACTED]
Principal Investigator	[REDACTED]
Number of sites	Minimum 4, Up to 10 (USA)
Vaccination dose, schedule and administration route	
Prime with Modified Vaccinia Ankara-Bavarian Nordic (MVA-BN)-Brachyury given subcutaneously (SC) for one dose each on Day 0 and Day 14. Administer each dose as four separate 0.5 mL injections (for a total dose of at least <math>5 \times 10^7</math> Inf.U) one in each arm, one in each leg using professional standards and practices.
 
Boost with Fowlpox Virus (FPV) -Brachyury given SC on Day 28, then every 4 weeks for 4 doses (End of Radiation +2, 6, 10, and 14 weeks), then given every 12 weeks (End of Radiation +26, 38, 50, 62, 74, 86, 98, and 110 weeks). One dose = one 0.5 mL injection with a nominal titer of <math>1 \times 10^9</math> Inf.U per 0.5 mL.

Trial duration	The total duration of the trial for each patient is up to 29 months
Trial population	Patients at least 12 years old with advanced chordoma who are planning to be treated with radiotherapy to at least one lesion. Patients will have no history of autoimmune disease (with exceptions detailed in the exclusion criteria below), will have measurable disease as defined by Response Evaluation Criteria in Solid Tumors (RECIST) 1.1, and will have adequate organ function
Number of patients	Planned trial size is based on a Simon 2-stage design, in which 10 patients are treated initially. If $\geq 1$ patient(s) in the first 10 have an objective response [partial response (PR) or complete response (CR)] by RECIST 1.1, an additional 19 patients may be enrolled for a total of 29 patients. Otherwise, the trial will be stopped. If 4 or more objective responses are observed in 29 patients, the null hypothesis that the true Objective Radiographic Response Rate (ORR) anytime within 12 months post completion of radiation is 5% or less will be rejected. This

design yields a one-sided type I error rate of 5% and power of 80% when the true response rate is 20%.

---

#### Primary objectives

To determine if the combination of BN-Brachyury administered with radiotherapy will result in a clinically meaningful ORR when compared with historical control.

---

#### Secondary objectives

- To confirm the safety profile of BN-Brachyury plus radiation therapy
- Progression Free Survival (PFS) by modified RECIST 1.1 criterion
- Improvement in clinical symptoms as measured by the Brief Pain Inventory (Short Form) [BPI-SF] pain assessment

---

#### Exploratory objectives

- Evaluate the differences in clinical outcome measures by location of primary tumor (Sacral vs. Mobile Spine vs. Clival)
- Measure adverse event profile by location of primary tumor
- To evaluate other clinical endpoints that might be indicative of clinical benefit:
  - ORR by standard RECIST 1.1
  - PFS by other criteria [Choi ([Choi, 2007](#)), volumetric ([Fenerty et al., 2016](#)), standard RECIST 1.1]
- To evaluate changes in immune and tumor related biomarkers of pre- versus post-baseline samples
  - Peripheral blood mononuclear cells (PBMC)
    - Brachyury and other Tumor associated antigen (TAA) specific T cell activation
    - Immune cell subset quantification and characterization
  - Serum
    - Analysis for soluble factors associated to immune response e.g. antibodies or cytokines

---

#### Primary endpoints

ORR anytime within 12 months post completion of radiation on target lesion(s) based on modified RECIST 1.1. Refer to [Section 10.5](#) for the response criteria.

---

#### Secondary efficacy endpoints

- PFS by modified RECIST 1.1
- Improvement in clinical symptoms measured by the BPI-SF

---

#### Safety endpoints

- Injection site reaction
- Other adverse events
- Clinically significant shifts in chemistry and hematology laboratory values

Exploratory endpoints	
 
• ORR anytime post completion of radiation on all lesions by standard RECIST 1.1
 
• ORR anytime within 12 months post completion of radiation on target lesion(s) based on Choi (Choi, 2007) criteria and volumetric criteria
 
• PFS based on all lesions by standard RECIST 1.1
 
• PFS based on target lesion(s) by Choi (Choi, 2007) criteria and volumetric criteria
 

Trial design	
This is a single arm Phase 2 clinical trial using a Simon 2-stage optimal design. The goal is to demonstrate that BN-Brachyury plus radiation therapy can induce objective radiographic responses in patients. In stage 1, a minimum threshold of activity will be needed to proceed to stage 2.

Inclusion criteria	
 
1. Diagnosis: Patients must have histologically confirmed chordoma by the pathology department of the site to enroll the patient on trial, which is metastatic or unresectable locally advanced. Patients with potentially curable disease are eligible if the patient refuses therapy with curative intent and all other eligibility criteria are met.
 
2. Patients must have measurable disease by RECIST 1.1 (Appendix 1).
 
3. Patient must be scheduled to have radiation therapy to at least 1 target lesion with a minimum biologic equivalence of 8Gy in 1 fraction (see Section 6.3.1.1 for equivalent doses). Any lesion irradiated within the previous 1 year cannot be a RECIST 1.1 target lesion.
 
4. Eastern Cooperative Oncology Group (ECOG) performance status of 0 to 2 at trial entry (See Appendix 2).
 
5. Age <math>\geq</math> 12 years.
 
6. Patients must have normal organ and marrow function as defined below: 
 
a. Serum creatinine <math>\leq</math> 1.5 x upper limit of normal OR creatinine clearance on a 24-h urine collection of <math>\geq</math> 60 mL/min.
 
b. Alanine Aminotransferase (ALT) and Aspartate Aminotransferase (AST) <math>\leq</math> 2.5 x the upper limit of normal.
 
c. Total bilirubin <math>\leq</math> 1.5 x upper limit of normal OR in patients with Gilbert's syndrome, a total bilirubin <math>\leq</math> 3.0 x upper limit of normal.
 
d. Hematological eligibility parameters (within 16 days of initiating treatment): 
 
i. Granulocyte count <math>\geq</math> 1,500/mm^3
 
ii. Platelet count <math>\geq</math> 100,000/mm^3
 
iii. Resting Pulse oximetry <math>></math> 90% on room air.
 
 
 
 
 
7. Must have recovered completely (Grade 1, stable, baseline) from any reversible toxicity associated with recent therapy. Typically,
 

this is 3–4 weeks for patients who most recently received cytotoxic therapy, except for the nitrosoureas and mitomycin C for which 6 weeks is needed for recovery.

8. There should be a minimum of 2 weeks from any chemotherapy, small molecule/targeted therapy, immunotherapy and/or radiation prior to start of trial treatment.
9. Females of child-bearing potential (FOCBP) and male partners of FOCBP must agree to use effective birth control or abstinence from screening up to and including the day of the last vaccination therapy.
10. Ability to understand and the willingness to sign a written informed consent or in the case of ages 12 to 17, an assent document.

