12. Pregnant women are excluded from this trial due to the unknown effects of the BN-Brachyury on the fetus or infant. Because there is an unknown but potential risk for adverse events in nursing infants secondary to treatment of the mother with BN-Brachyury, breastfeeding should be discontinued if the mother is treated with BN-Brachyury. These potential risks may also apply to other agents used in this trial.
13. Human immunodeficiency virus (HIV)-positive patients are ineligible because of the potential for decreased immune response to the vaccine.
14. Significant cardiovascular disease, which includes but is not limited to New York Heart Association Heart Failure Class II or greater, myocardial infarction within the previous 3 months, unstable arrhythmias, unstable angina.
  - a. Patients with known coronary artery disease, congestive heart failure not meeting the above criteria, or left ventricular ejection fraction < 50% on a stable medical regimen that was optimized in the opinion of the treating physician, in consultation with a cardiologist if appropriate, are eligible.

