##### 4.2.1.2 Laboratory Studies

To be performed at any time before Screening/ Baseline:

- Confirmation of diagnosis by Site Pathology Department.

To be performed within 6 months prior to Screening/ Baseline:

- Screening for HIV
- Screening for Hepatitis B and C.

To be performed within 16 days prior to Screening/ Baseline:

- Complete blood count plus differential and platelet count
- Serum chemistries (Na+, K+, Cl, CO2, glucose, BUN, creatinine, albumin, calcium, alkaline phosphatase, ALT, AST, total bilirubin, TSH)
- Antinuclear antibody titer (ANA)
- Beta-HCG for females of childbearing potential (repeated Beta-HCG [serum or urine] tests within 48 hours prior to treatment). Females of childbearing potential: A female of childbearing potential is a woman who:
  - Has started menses
  - Has not undergone a hysterectomy or bilateral oophorectomy
  - Has not been naturally postmenopausal for at least 24 consecutive months (i.e. has had menses at any time in the preceding 24 consecutive months)
  - Women of childbearing potential and sexually active males must be strongly advised to use an accepted and effective method of contraception or to abstain from sexual intercourse for the duration of their participation in the trial
- CD4:CD8 ratio, CD3, 4, 8, 19 subsets and Natural Killer (NK) markers (baseline, about day 28 and around day 85 prior to vaccination)

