## 4.2.3 After Treatment Completion

Post-treatment follow-up will be conducted 30 (+/- 2) days after last dose of treatment. The visit should include a history and physical exam; labs with CBC/differential and serum chemistries; assessment of trial drug AEs; RECIST 1.1 assessment; and CT chest, abdomen, and pelvis, and MRI (if target lesion is best visualized by MRI). If patient had abnormal physical exam findings or abnormal lab values at the off-treatment time point, then the patient should have follow-up visit with the primary oncologist to focus on the abnormal finding(s). Results and report findings should be faxed or emailed to the trial team.

Once the 30 day follow up assessment is completed, the patient is then taken off trial.

Patients removed from trial for any reason must be followed for at least 30 days after the last dose of vaccine or until all toxicities have resolved to baseline or stabilized, whichever is later.

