### 5.2 Inclusion Criteria

A subject will be eligible for inclusion in this trial if ALL of the inclusion criteria apply. Refer to Trial Synopsis ([Section 1.4](#)).

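### Inclusion 9 ends the required contraception agreement on the day of the last vaccination, while Section 4.2.1.2 advises contraception to the end of participation, 28 to 32 days later on schedule

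*Protocol*

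**What the plan says.** Two clauses of the protocol set a stop date for contraception.

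- **Eligibility condition.** Inclusion criterion 9 (Section 1.4, Synopsis) says that FOCBP and male partners of such women "must agree to use effective birth control or abstinence from screening up to and including the day of the last vaccination therapy". Section 5.2 makes this a condition of entry: "A subject will be eligible for inclusion in this trial if ALL of the inclusion criteria apply".
- **Advice.** Section 4.2.1.2 (Laboratory Studies), in the list attached to the pregnancy test, states: "Women of childbearing potential and sexually active males must be strongly advised to use an accepted and effective method of contraception". Abstinence is offered as the alternative, and the advice is set to last as long as the patient takes part in the trial.

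The end of participation follows from Section 4.2.3: "Post-treatment follow-up will be conducted 30 (+/- 2) days after last dose of treatment", and "Once the 30 day follow up assessment is completed, the patient is then taken off trial". The schedule in Section 1.5 gives the same 2-day window. Section 4.2.5 adds that patients who come off treatment because of toxicity stay in follow-up until the toxicity resolves and the disease progresses.

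Two further places bear on the point. Exclusion criterion 12 gives the reason for caution: "Pregnant women are excluded from this trial due to the unknown effects of the BN-Brachyury on the fetus or infant". Section 9.5.4 makes a pregnancy reportable if it occurs up to 30 days after a vaccine dose, and once calls this one month with a minimum of 30 days.

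The SAP adds nothing. Its Section 1.4 refers back to the protocol for the eligibility criteria.

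**The concern.** The patient is given two stop dates for the same precaution, and the one agreed to as a condition of entry is the earlier. A patient who keeps only to inclusion 9 may stop contraception on the day of the final dose and still be compliant with it. For the remaining weeks on trial, only the Section 4.2.1.2 advice asks for contraception, and it sits under a laboratory heading where it is easily overlooked.

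What is at stake is a conception soon after a dose of a product whose fetal effects the protocol itself calls unknown. Section 9.5.4 also names exposure through semen, so men are concerned as well. Inclusion 9 is unclear about them: its reference to men can be read as male patients with an FOCBP partner, or as partners of female patients who are not themselves in the trial.

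This is a point of patient safety and consistent wording. Sample size, error rates and the efficacy analysis are not affected.

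**Working it through.** There is no stated figure to reproduce. The check is calendar arithmetic on the protocol's own windows. Let L be the day of the last vaccination and V the day of the post-treatment visit.

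| Item | Source | End point |
|---|---|---|
| Required agreement | Inclusion 9 | L |
| Contraception advice | 4.2.1.2 with 4.2.3, scheduled path | V = L + 30 (+/- 2), so L + 28 to L + 32 |
| Contraception advice, early stoppers | 4.2.3 and 4.2.5 | Can pass L + 32; no upper limit given |
| Pregnancy reporting | 9.5.4 | At least L + 30 |

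**1. Difference between the two contraception clauses.** (L + 28) - L = 28 days and (L + 32) - L = 32 days. This assumes that the last treatment is a vaccination and that the final visit is on schedule.

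**2. Early stoppers.** The advice lasts as long as participation. For patients kept in follow-up under Section 4.2.5, or followed under Section 4.2.3 until toxicities resolve or stabilize, the difference can exceed 32 days. The documents do not allow a figure.

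**3. Reporting window.** (L + 30) - L = 30 days. This only locates the window. Section 9.5.4 says which pregnancies to report and sets no contraception period.

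**4. Radiotherapy.** On the Synopsis timetable the last vaccine is at end of radiation + 110 weeks: 110 x 7 = 770 days, or 756 to 784 with the 2-week window. Section 4.2 numbers doses only to 13. Counting six 12-weekly doses from week 26 gives week 26 + 5 x 12 = 86, or 86 x 7 = 602 days. Either way inclusion 9 covers all of radiotherapy on the scheduled path. The exception is a patient who stops vaccine before or during radiotherapy: the agreement has then lapsed for the rest of it. No day count is possible, because the length of radiotherapy is set case by case.

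**5. After the proposed change.** The agreement would end at the later of V and L + 30 when the last treatment is a vaccination.
- V = L + 28: the agreement ends at L + 30, which is 30 - 28 = 2 days after the advice.
- V = L + 32: the agreement ends at L + 32, together with the advice.

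The scheduled difference is closed, and the agreement reaches at least L + 30 in every case. The added requirement is 30 to 32 days. Patients followed beyond the visit would depend on the advice for the remainder, as they do now.

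**The case against.** The strongest reply is that the protocol already has a contraception provision for these weeks. Section 4.2.1.2 runs to the end of participation and reaches all sexually active males, which is wider than inclusion 9. A reader might infer that the month after the final dose is left with no contraception measure. The documents do not support that: the advice applies, and what differs is the strength of the two clauses. This part of the reply stands.

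The contrast in strength is also thinner than it looks. Inclusion 9 is an agreement given at entry. The protocol describes no later check on contraceptive use and no consequence for stopping. Both clauses rely on the patient. That is fair, but a condition of entry is still the firmer of the two, and there is no evident reason for it to end first.

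Three other stronger readings are tempting and should not be taken.

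- **That Section 9.5.4 contradicts inclusion 9.** It is a reporting window, in line with the 30-day collection of adverse events in Sections 8.1.1 and 9.5.2. A reporting period may outlast a contraception period without conflict. It supports 30 days as a convenient end point and no more.
- **That 30 days is biologically required.** Section 2.5.1 describes the MVA-BN vector as unable to replicate in almost all human cell lines and fowlpox vectors as not replicating in human cells. Nothing in the documents derives a contraception period.
- **That pregnancy testing is tied to vaccination alone.** Footnote 6 of the schedule also requires a test within 48 hours of radiation, and the row is marked at Day 42-70. The test is absent from the post-treatment visit, both in the schedule and in the contents that Section 4.2.3 lists: "The visit should include a history and physical exam; labs with CBC/differential and serum chemistries; assessment of trial drug AEs; RECIST 1.1 assessment", followed by imaging. The present point does not depend on that absence, and the fix adds no test.

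Finally, the consent form is not among the documents and may already give a single stop date. That limits what can be said about practice, but not the mismatch in the protocol text.

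**Conclusion.** The point holds as a mismatch between two clauses. The eligibility condition ends on the day of the last vaccination, and the advice ends 28 to 32 days later on the scheduled path, or later still for some early stoppers. No text in the protocol or SAP extends the agreement. The weaker clause is the longer one, which sits poorly with exclusion 12.

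Severity is minor. The interval is covered by advice, and no endpoint or analysis is involved. The number affected is not given and is probably small: 29 evaluable patients are planned and incidence peaks between the fourth and sixth decades (Section 2.2), though entry is open from age 12.

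The day count assumes that the last treatment is a vaccination and that the final visit falls in its window. The practical consequence also depends on the consent wording, which could not be checked.

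**What to change.** Amend inclusion 9 so that FOCBP, and male patients with an FOCBP partner, agree to effective contraception or abstinence starting at screening and lasting until the post-treatment follow-up visit or 30 days after the last trial treatment (vaccine or radiation), whichever is later. This aligns the two stop dates on the scheduled path, covers a patient whose last treatment is radiation, and makes clear which men are meant.

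Leave the Section 4.2.1.2 advice as it is. It is broader, and it still serves patients followed beyond the visit. Put the same wording in the consent and assent forms. An amended entry criterion does not by itself reach patients already enrolled, so for them the consent text is the working route.

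The cost is a written amendment, which Section 16 sends to the local IRB, the coordinating investigator and each site's principal investigator (4 to 10 sites are planned), plus about 30 more days of required contraception for a small number of patients. No visit, test or analysis is added.

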#### Exclusion criteria

Patients with any of the following will not be eligible for participation in this trial:

1. Concurrent systemic treatment for cancer.
2. Patients with rapidly progressing disease at multiple sites
3. Patients with poorly differentiated or dedifferentiated chordomas
4. Chronic hepatitis B or C infection, because potential immune impairment caused by these disorders may diminish the effectiveness of this immunologic therapy.
5. Any significant disease that, in the opinion of the investigator, may impair the patient's tolerance of trial treatment.
6. Significant dementia altered mental status, or any psychiatric condition that would prohibit the understanding or rendering of informed consent.
7. Active autoimmune diseases requiring treatment or a history of autoimmune disease that might be stimulated by vaccine treatment. This requirement is due to the potential risks of exacerbating autoimmunity. However, patients with vitiligo or clinically stable autoimmune endocrine disease (i.e.: Hashimoto's thyroiditis) who are on appropriate replacement therapy (if such therapy is indicated) are eligible.
8. Concurrent use of systemic steroids, except for physiologic doses of systemic steroid replacement or local (topical, ophthalmic, nasal, or inhaled) steroid use. Limited pharmacologic doses of systemic steroids (e.g., in patients with exacerbations of reactive airway disease or to prevent intravenous (IV) contrast allergic reaction or anaphylaxis in patients who have known contrast allergies) are allowed.
9. Patients who are receiving any other investigational agents within 28 days before start of trial treatment.
10. History of allergic reactions attributed to compounds of similar chemical or biologic composition to MVA-BN ®/FPV-Brachyury or other agents used in trial. History of allergic reaction to aminoglycoside antibiotics or egg products.
11. Serious or uncontrolled intercurrent illness including, but not limited to, ongoing or active infection, symptomatic congestive heart failure, unstable angina pectoris, cardiac arrhythmia, or

---

psychiatric illness/social situations that, in the opinion of the investigator, would limit compliance with trial requirements.

12. Pregnant women are excluded from this trial due to the unknown effects of the BN-Brachyury on the fetus or infant. Because there is an unknown but potential risk for adverse events in nursing infants secondary to treatment of the mother with BN-Brachyury, breastfeeding should be discontinued if the mother is treated with BN-Brachyury. These potential risks may also apply to other agents used in this trial.
13. Human immunodeficiency virus (HIV)-positive patients are ineligible because of the potential for decreased immune response to the vaccine.
14. Significant cardiovascular disease, which includes but is not limited to New York Heart Association Heart Failure Class II or greater, myocardial infarction within the previous 3 months, unstable arrhythmias, unstable angina.
  - a. Patients with known coronary artery disease, congestive heart failure not meeting the above criteria, or left ventricular ejection fraction < 50% on a stable medical regimen that was optimized in the opinion of the treating physician, in consultation with a cardiologist if appropriate, are eligible.

